Study Title: Evaluation of a Sirolimus Eluting Bioadaptor as Compared to a Zotarolimus Eluting Stent in *De novo* Native Coronary Arteries

NCT Number: NCT04192747

Protocol Number: ELX-CL-1805

Date: 20 July 2022

Revision: 1.4 (Japan) and 1.4.1 (Europe)

Title	Evaluation of a Sirolimus Eluting Bioadaptor as Compared to a Zotarolimus Eluting Stent in De novo Native Coronary Arteries (referred to as “Bioadaptor RCT”)
Objective	The objective of this study is to verify the safety and efficacy of the investigational device (ELX1805J) for the treatment of ischemic heart disease due to de novo , native coronary artery lesions
Study design	
A prospective, multicenter, randomized (1:1; DynamX Bioadaptor (ELX1805J): Resolute Onyx), single-blind study, registering approximately 444 subjects at approximately 35 sites within Japan, Europe, and New Zealand to be conducted in two parallel cohorts. The combined Japan Bioadaptor RCT data and European Bioadaptor RCT data are intended to serve as the pivotal trial to support the regulatory approval in Japan with the Pharmaceuticals and Medical Devices Agency (PMDA).
 
Up to 2 de novo lesions located in 2 separate native coronary arteries designated as target lesions may be treated. The target lesion(s) must measure between 2.25 mm and 4.0 mm in diameter and ≤ 34 mm in length, to be covered by a single ELX1805J Bioadaptor or a single control device. Patients should not be randomized until after satisfactory pre-dilatation of the target lesion has been performed.
 
A non-target lesion may be treated if located in separate epicardial vessel (RCA, LCX or LAD) using an approved ‘olimus drug eluting stent provided the treatment of this non-target lesion is done prior to the treatment of the target lesion(s), and the treatment of the non-target lesion is considered successful. The segment should be located such that any injury that might occur during intervention can be clearly attributable to that treated segment.
 
Japanese Cohort (222 subjects) & European/New Zealand Cohort (222 subjects) The study is composed of two cohorts, i.e., the Japanese cohort and the European/New Zealand cohort. For each cohort, at least 222 subjects are randomly allocated in a 1:1 ratio to either the test or control arm. All subjects will receive follow-up clinical assessments at 1, 6 and 12 months and every year for 5 years thereafter. Additionally, imaging follow-up with IVUS and IVUS + OCT are collected in the following imaging subsets. Data from the Bioadaptor RCT European Cohort will be pooled with the data from the Bioadaptor RCT Japan Cohort to support primary and secondary endpoints. The primary endpoint analysis will be performed using the Intent-to-Treat (ITT) population on all subjects at the point of randomization.

	
IVUS Imaging Subset (80 subjects in the Japanese cohort) The IVUS imaging subset of approximately 80 subjects undergo angiography and IVUS assessments at baseline and 12 month follow-up.
 
IVUS + OCT Imaging Subset (20 subjects in the Japanese cohort) The IVUS + OCT imaging subset of approximately 20 subjects undergo angiography, IVUS + OCT assessments at baseline and 12 month follow-up.
 
Single-group study (referred to as PK substudy) Up to 2 de novo lesions located in 2 separate native coronary arteries designated as target lesions may be treated. The PK study will enroll 8 Japanese subjects and is being conducted to assess the blood pharmacokinetics of Sirolimus eluted from the ELX1805J Bioadaptor implanted in patients. PK measurement will be conducted at pre-treatment, 10 minutes, 30 minutes, 1, 2, 4, 6, 12, 24, 72 hours, and 7 days. In addition, all subjects will undergo clinical follow-up assessments at 1, 6 and 12 months and every year for 5 years thereafter.

Enrollment/ Number of Sites	
Approximately 444 subjects will be enrolled at up to 35 centers in Japan and Europe/New Zealand.
 
Planned: Japanese cohort: 222 European/New Zealand cohort: 222 PK substudy: 8

Study Devices	
Investigational device: ELX1805J (Japan); DynamX Sirolimus Eluting Coronary Bioadaptor System (Europe/NZ)
 
Control device: Resolute Onyx Zotarolimus Eluting Coronary Stent System (Medtronic Japan Co., Ltd. or Medtronic per the applicable geography)
 
PK study: Subjects are to receive the ELX1805J device

Clinical Endpoints:	
Primary Endpoint: Target lesion failure (TLF) assessed at 12 months. TLF is a composite endpoint defined as cardiovascular death, target-vessel MI, and clinically-indicated target lesion revascularization (CI-TLR)
 
Secondary Endpoints: Efficacy endpoints
 
 • Acute success rates: Lesion success rate, device success rate, procedure success rate

	
Clinical endpoints
 
Measured at 30 days, 6 months, 12 months, 2, 3, 4 and 5 years:
 
 • TLF • Patient Oriented Clinical Endpoint: Overall cardiovascular outcomes from the patient’s perspective. This endpoint is a composite endpoint that includes all-cause mortality (cardiac and non-cardiac), stroke, MI (target vessel and non-target vessel) and revascularization (target vessel and non-target vessel) • A composite of all-cause mortality, MI (target vessel or non-target vessel) and revascularization (target vessel or non-target vessel) • Composite of cardiovascular death, target vessel myocardial infarction (TV-MI)*, or clinically-indicated target vessel revascularization (CI-TVR) • Composite of cardiovascular death, stroke, MI (target vessel or non-target vessel) and revascularization (target vessel or non-target vessel) • Composite of cardiovascular death, MI (target vessel or non-target vessel) and revascularization (target vessel or non-target vessel) • Clinically-indicated target lesion revascularization (CI-TLR)TLR • Target vessel revascularization (TVR) • Clinically-indicated TVR (CI-TVR) • Revascularization (target vessel or non-target vessel) • Q-wave MI • Non Q-wave MI • MI (target vessel or non-target vessel) • Target vessel MI • Cardiovascular death • All-cause death • Composite of cardiovascular death or target vessel MI • Composite of all-cause death or MI(target vessel or non-target vessel) • Composite of all-cause death, MI(target vessel or non-target vessel), or TVR • Composite of probable or definite stent thrombosis‡ • Probable stent thrombosis‡ • Definite stent thrombosis‡ 
* Defined as myocardial infarction not clearly attributed to a non-target vessel
 
‡ Defined as per the Academic Research Consortium (ARC-2) criteria

Imaging Endpoints
	
QCA endpoints:
 
 • Acute recoil • Late lumen loss (in-stent and in-segment) at 12-month follow-up

QCA, IVUS, and OCT	
 • Change in vessel angulation from baseline, post-stent and 12-month follow-up • MLD post-procedure and 12 months • % DS post-procedure and 12 months 
IVUS endpoints:
 
 • Change in mean lumen area from post-procedure to 12-month follow-up • In-stent % neointimal obstruction at 12-month follow-up • In-stent late lumen loss at 12-month follow-up • Acute, persistent and late stent malapposition 
OCT Endpoints:
 
 • % Strut coverage • Neointimal thickness • Vessel Pulsatility - % change in Lumen Area and Device Area during systole and diastole by stationary OCT • Additional parameters may be assessed
Key Inclusion Criteria	
Patients who meet all of the following criteria are eligible:
 
 • Patient must be ≥ 20 years of age. • Patient must have evidence of myocardial ischemia (e.g., stable or unstable angina, silent ischemia, positive functional study or electrocardiogram (ECG) changes consistent with ischemia) • Patients who are able to take dual anti-platelet therapy for 1 year following the index procedure and anticoagulants prior to/during the index procedure • The subject is an acceptable candidate for Percutaneous Transluminal Coronary Angioplasty (PTCA), stenting, and emergent Coronary Artery Bypass Graft (CABG) surgery. • The subject or subject's legally authorized representative has been informed of the nature of the study and agrees to its provisions and has provided written informed consent as approved by the Institutional Review Board or Ethics Committee of the respective clinical site. • Women of childbearing potential with a negative pregnancy test within 7 days and women who are not pregnant or nursing • Patient must agree to undergo all clinical study required follow up visits, angiograms, and imaging testing • Patient must agree not to participate in any other clinical research study for a period of one year following the index procedure

	
Angiographic inclusion criteria- Target Lesion/Vessel
 
Confirmed in QCA assessment:
 
 Target lesion(s) must be de novo and located in a native coronary artery with a vessel mean diameter of ≥ 2.25 and ≤ 4.0 mm assessed 
Confirmed by visual assessment:
 
 Target lesion(s) must be in a major artery or branch with a visually estimated stenosis of $\geq 50\%$ and $< 100\%$ with a TIMI flow of >1. When two target lesions are treated, they must be located in separate major epicardial vessels The visually estimated target lesion length is ≤ 34 mm and must be able to be covered by a single 14/15/18/23/28/32/38 mm ELX1805J stent and have at least 2 mm of healthy vessel on either side, OR The visually estimated target lesion length is ≤ 34 mm and must be able to be covered by a single 15/18/22/30/34/38 mm ZES stent respectively and have at least 2 mm of healthy vessel on either side The lesion(s) must be successfully pre-dilated prior to enrollment Mandatory pre-dilatation includes the use of 2 orthogonal views to confirm lesion inclusion and exclusion criteria. Successful pre-dilatation of a minimum of 1 Target Lesion, defined as no waist in the inflated pre-dilatation balloon (using two orthogonal views) with a pre-dilatation balloon diameter size approximately 0.25 mm smaller than reference vessel diameter but not more than 0.5 mm smaller than the reference vessel diameter. A residual diameter stenosis prior to study device implantation by visual estimate is recommended to be $<30\%$. Percutaneous intervention of lesions in a non-target vessel if: 
 Not part of another clinical investigation ≥ 30 days prior to the study index procedure ≥ 6 months after the study index procedure (planned) Percutaneous intervention of lesions located in the target vessel if: 
 Not part of a clinical investigation ≥ 6 months prior to the study index procedure ≥ 12 months after the study index procedure (planned) Previous intervention was distal to and >10 mm from the target lesion 
Additional inclusion Criteria for PK study Patients participating in PK study may be treated with only ELX1805J


Key Exclusion Criteria
	
Patients must not have any of the following:
 
 The patient was diagnosed with an acute myocardial infarction within the past 72 hours and the CK and CKMB have not returned to normal (or cTn $>15x$ ULN) and the patient is experiencing clinical symptoms indicative of ongoing ischemia

- Patient has a known hypersensitivity or contraindication to aspirin, both heparin and bivalirudin, clopidogrel, prasugrel or ticagrelor, cobalt, nickel, chromium, molybdenum, PLLA polymers or contrast sensitivity that cannot be adequately pre-medicated
- Patients with a history of allergic reaction or serious hypersensitivity to drugs exhibiting interactions with sirolimus, zotarolimus, everolimus, tacrolimus, temsirolimus, biolimus and other rapamycin, derivatives or analogues) or similar drugs
- Elective surgery is planned within the first 6 months after the procedure that will require discontinuing either aspirin or clopidogrel or other P2Y12 inhibitors
- Patient presenting with chronic (permanent) atrial or ventricular arrhythmia or current unstable ventricular arrhythmias
- Patient has a known left ventricular ejection fraction (LVEF) < 30%
- Patient has received a heart or other organ transplant or is on a waiting list for any organ transplant
- Patient has a malignancy that is not in remission.
- Patient is receiving immunosuppression therapy other than steroids and has known immunosuppressive or autoimmune disease (e.g. human immunodeficiency virus, systemic lupus erythematosus etc.)
- Patient is receiving chronic anticoagulation therapy (e.g., heparin, coumadin) that cannot be stopped and restarted according to local hospital standard procedures
- Patient has a platelet count < 100,000 cells/mm³ or > 700,000 cells/mm³, a WBC of < 3,000 cells/mm³, or documented or suspected to have cirrhosis of Child-Pugh ≥ Class B within 7 days before study procedure
- Patient has known renal insufficiency (e.g., serum creatinine level of more than 2.5 mg/dL within 7 days before study procedure, or patient on dialysis)
- Patient has a history of bleeding diathesis or coagulopathy or will refuse blood transfusions
- Patient has had a cerebrovascular accident (CVA) or transient ischemic neurological attack (TIA) within the past six months
- Patient has had a significant GI or urinary bleed within the past six months
- Patient has severe symptomatic heart failure (i.e., NYHA class IV)
- Patient has a medical condition that precludes safe 6 French sheath insertion
- Patient has other medical illness or known history of substance abuse (alcohol, cocaine, heroin etc.) that may cause non-

compliance with the clinical study plan, confound the data interpretation or is associated with a limited life expectancy (i.e., less than one year)

- Patient is already participating in another clinical research study which has not reached the primary endpoint (long-term follow-up is not an exclusion)
- Other patients whom primary investigator or sub-investigator determined to be ineligible for this clinical study

Angiographic exclusion criteria

- Patients with bypass graft to the target vessel or lesion is located in a bypass graft
- Patients with stent implanted within 10 mm of proximal or distal end of target lesion
- Patients with a target lesion involving a bifurcation of which the side branch will be jailed by the struts and:
 - Side branch > 2.5 mm in diameter
 - Side branch requires planned predilatation (including Kissing Balloon Technique), or Side branch has an ostial lesion or lesion with > 50% stenosis
- Patients suspected or confirmed with the QCA analysis of having stenotic lesion of more than 50% in target vessel in addition to target lesion
- Patients with target lesion in ostia located within 5 mm of origin of LAD, LCX or RCA
- Patients with stenotic lesion in left main trunk
- Patients with target lesion that is a chronic total occlusion (CTO) or \leq TIMI 1 coronary flow in the target vessel
- Patients with target vessel that contains thrombus as indicated in pre-procedure angiographic, IVUS or OCT images
- Excessive tortuosity \geq two 45° angles or extreme angulation (\geq 90°) proximal to or within the target lesion
- Patients with target vessel that has moderate to severe calcification that prevents complete angioplasty balloon (POBA with non-compliant balloon, or scoring balloon,) inflation or requires other devices such as rotational atherectomy, rotablator.
- Patients with dissection of Grade A or B that cannot be covered (including 2 mm distal to the dissection) with a single study device or with dissection of Grade C or higher
- Patients with 2 or more target lesions on 1 branch or target lesions on 3 branches that need to be treated during study procedure
- Target lesion involves a myocardial bridge

	
Additional Exclusion Criteria for PK study
 
 • Patients with following criteria 
 ○ Patient with PCI within 180 days before study procedure ○ Patient with plan to have staged PCI within 90 days after study procedure ○ Patients who have non-target lesion

Statistical Methods
	
The analysis of primary endpoint and secondary endpoints are performed using the Intention-To-Treat (ITT) population. The analysis of secondary clinical endpoints are conducted with the Per-Treatment Evaluable (PTE) population in addition to the ITT population.
 
Analysis of the Primary Endpoint
 
Study success is defined as successful rejection of the null hypothesis for the primary endpoint. The primary endpoint for the study is TLF at 12 months post treatment. The primary endpoint will be evaluated using the ITT population for study success and may also be carried out on the PTE population. The null hypothesis for this study is that the ELX1805J arm will have a 12-month TLF rate that exceeds that of the control device arm by at least a pre-specified margin of 6 (delta). The alternative hypothesis is that the ELX1805J arm will have a 12-month TLF rate that is no more than that of the control device, or exceeds that of the control device but by less than 6. Rejection of the null hypothesis will signify that the ELX1805J is non-inferior to the control device with regard to 12-month TLF. The null hypothesis (Ho) and the alternative hypothesis (Ha) can be expressed as below:
 
Ho: $\pi_A \geq \pi_C + 8.6\%$
 
Ha: $\pi_A < \pi_C + 8.6\%$
 
Here, π_A is a true TLF Rate of investigational device, and π_C is a true TLF Rate of control device.
 
Based on non-inferiority test for an endpoint that follows binomial distribution, in addition to difference between TLF rates at 12 months for 2 groups (investigational device - control device), one-sided 95% confidence interval of the difference in TLF is

calculated. Tests are conducted using normal approximation of binomial distribution. When the upper limit of this confidence interval is less than 8.6% (delta of non-inferiority), the null hypothesis is rejected, confirming non-inferiority of investigational device compared to control device for TLF rate at 12 months. This primary analysis will be conducted using the ITT population. Handling of missing data is described in section 3.4.1. In addition, Kaplan-Meier curve for time till first event considered to be TLF will be done. If multiple TLF occurred in same case, occurrence date of the first TLF is the occurrence date of TLF. During study procedure, up to 2 lesions in different epicardial vessels may be treated with the assigned study device. When there are multiple TLF, in a single case, it is counted per case (counted as single incidence).

Analysis of the Secondary Endpoints

Time-dependent response variables can be expressed using Kaplan-Meier curve, and differences in these variables between groups are tested using log-rank test. Data for all categorical endpoints (e.g., TLF rate at a specific time point, etc.) are shown with number of patients, percentage and Clopper-Pearson's exact 95% confidence interval. Differences between treatment groups are shown using 95% confidence interval of the difference. Comparison of imaging corelab endpoints (QCA, IVUS and OCT) in the Japanese cohort will also use the difference between treatment groups and the 95% confidence interval of the difference. Analyses of clinical secondary endpoints are conducted with the PTE population in addition to the ITT population.

Sponsor

Elixir Medical Corporation
 [name]
 [name]
 USA

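### Subjects are allocated 1:1 within each of two cohorts, but the pooled log-rank tests and the primary TLF difference name no cohort stratum: a small efficiency loss, without bias

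*Combined protocol and SAP*

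**What the plan says.** Study design describes two parallel cohorts and fixes allocation within each: "For each cohort, at least 222 subjects are randomly allocated in a 1:1 ratio to either the test or control arm". The cohorts are then combined: "Data from the Bioadaptor RCT European Cohort will be pooled with the data from the Bioadaptor RCT Japan Cohort", in support of both primary and secondary endpoints.

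Under Analysis of the Primary Endpoint, the estimate is the "difference between TLF rates at 12 months for 2 groups" (test minus control) with a one-sided 95% confidence limit. On method the section says "Tests are conducted using normal approximation of binomial distribution". No cohort term appears.

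Under Analysis of the Secondary Endpoints, time-dependent variables are compared between groups by a log-rank test, again with no stratum. The secondary clinical endpoints are "Measured at 30 days, 6 months, 12 months, 2, 3, 4 and 5 years", so these comparisons run to 5 years. The only cohort that Statistical Methods names is the Japanese one, for the imaging endpoints.

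The text also points to a section that is not in the document: "Handling of missing data is described in section 3.4.1". That pointer describes missing-data handling only.

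**The concern.** When allocation is balanced within known groups, the analysis ordinarily reflects those groups. If it does not, variation between cohorts stays in the error term. The standard error of the pooled difference is then slightly too large. In a log-rank test over several years, the mixing of low-risk and high-risk subjects also makes the test conservative and weakens it. What is at stake is some precision and power, mainly in the 5-year time-to-event comparisons. There is also a procedural benefit: if cohort handling is fixed in advance, nobody has to choose it after seeing the data of a pooled trial intended as pivotal.

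**Working it through.** **Inputs.** From the document: 222 subjects per cohort, 1:1, so 222/2 = 111 per arm per cohort and 2 × 111 = 222 per arm pooled; one-sided 95% limit; follow-up to 5 years. The document gives no expected TLF rate, power or dropout, so the total of 444 cannot be re-derived. All event rates and the hazard ratio of 0.6 below are assumptions, shown over a range.

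**Bias.** With no treatment effect and cohort rates a and b, each arm has expected rate (111a + 111b)/222, so the expected crude difference is 0. The same holds for cohorts of 300 and 222: both arms have (150a + 111b)/261.

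**Standard error of the primary difference, equal arms.**

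- Unstratified: sqrt(2p(1−p)/222), with p = (a+b)/2.
- Stratified: sqrt(0.5 × [a(1−a) + b(1−b)]/111).

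At 1%/8%, p = 0.045. Unstratified: sqrt(2 × 0.045 × 0.955/222) = 1.968 points. Stratified: sqrt(0.5 × [0.0099 + 0.0736]/111) = 1.939 points.

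| Cohort TLF rates | Unstratified SE (points) | Stratified SE (points) | Excess |
|---|---|---|---|
| 3%/5% | 1.860 | 1.858 | 0.1% |
| 2%/6% | 1.860 | 1.850 | 0.5% |
| 1%/8% | 1.968 | 1.939 | 1.5% |
| 1%/15% | 2.575 | 2.488 | 3.5% |

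**Primary decision** (2,000,000 simulated trials per scenario). With equal arms and the 8.6% margin, the crude and Mantel-Haenszel decisions differ in 0.01% of trials at 3%/5% and 0.6% at 1%/15%. With the margin of 6 that the same section also prints, the figures are under 0.01% and 1.6%. Type I error at the 8.6% margin is 5.70% crude and 5.71% stratified at 3%/5%. The excess over 5% is therefore due to the normal approximation and not to leaving cohort out. At 1%/15% it is 4.91% crude and 5.43% stratified.

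**Log-rank over 5 years** (constant hazards, no dropout, two-sided 5%, 100,000 simulated trials per scenario; unstratified vs stratified).

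| Yearly control rates | Type I error | Power at HR 0.6 | Power loss (points) |
|---|---|---|---|
| 3%/5% | 4.9% vs 5.0% | 52.6% vs 53.0% | 0.4 |
| 2%/6% | 4.4% vs 5.0% | 50.5% vs 52.1% | 1.6 |
| 1%/8% | 3.6% vs 5.1% | 51.0% vs 55.7% | 4.7 |
| 5%/10% (broader composite) | 4.6% vs 5.1% | 75.7% vs 76.7% | 1.0 |
| 4%/12% (broader composite) | 4.2% vs 5.2% | 75.7% vs 78.2% | 2.5 |

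A repeat simulation gave losses of 54.3 − 52.3 = 2.0 points at 2%/6% and 56.4 − 51.4 = 5.0 points at 1%/8%. Hence the rounded figures of 0.4, 2 and 5. The way a yearly rate is converted to a hazard moves the power level by up to about 2 points but leaves the pattern the same.

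**The case against.** The strongest reply is that nothing here is wrong. The crude difference is unbiased, the unstratified tests are valid, and no two parts of the plan conflict on this point. Study success rests on the primary endpoint alone, where the effect at similar cohort rates is practically nil. The log-rank tests are secondary, have no stated power target, and lose more than about 2 points at low event rates only if the cohorts differ by far more than anything the document suggests; one set of eligibility criteria serves both. The text also reads as a synopsis, where a stratification term is easily left out.

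Most of this stands, and it keeps the point small. It does not remove it: the cohort is the level at which the 1:1 ratio is fixed, and naming it in the analysis costs almost nothing.

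A reader might infer two stronger claims. The first is that ignoring cohort biases the treatment comparison or inflates type I error. With 1:1 allocation in each cohort the bias is zero, and the unstratified tests err, if at all, on the conservative side. The second is that the plan rules stratification out. It is silent, and fuller text may exist, although the one missing section it cites is described as dealing with missing data.

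**Conclusion.** The point holds as an optional improvement. The plan allocates within cohorts and pools them, and the available Statistical Methods text does not carry cohort into the log-rank tests or the primary difference. At a hazard ratio of 0.6, the loss in the 5-year log-rank tests is about 0.4, 2 and 5 power points at yearly rates of 3%/5%, 2%/6% and 1%/8%, and it is negligible when the cohorts have similar rates. The effect on the primary decision is negligible at similar cohort rates and remains small even at 1%/15%. These sizes depend on assumed rates, constant hazards, no dropout and 111 subjects per arm per cohort. The absence of bias rests only on the 1:1 allocation within each cohort. The two printed margins, 6 and 8.6%, are a separate and more serious matter that must be reconciled in its own right; this point does not depend on which applies.

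**What to change.** In Analysis of the Secondary Endpoints, add: *Log-rank tests on pooled data are stratified by cohort (Japan; Europe/New Zealand).*

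In Analysis of the Primary Endpoint, add: *As a prespecified sensitivity analysis, the Mantel-Haenszel weighted average of the within-cohort 12-month TLF differences is reported with Greenland-Robins variance and the same one-sided 95% limit.*

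Leave the primary method and the success rule as they are. If fuller text already deals with stratification, align these sentences with it.

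The cost is an SAP edit made before results by arm are tabulated. No new data are needed, because cohort is known for every subject.

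### For a subject with two target lesions, do the differing pre-dilatation lines leave the second lesion's target status open at randomisation?

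*Combined protocol and SAP*

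**What the plan says.** The Study design row of the synopsis allows up to two target lesions in separate native arteries and ties pre-dilatation to allocation: "Patients should not be randomized until after satisfactory pre-dilatation of the target lesion has been performed". It also allows a non-target lesion in a separate epicardial vessel to be treated, provided this is done before the target lesion or lesions are treated.

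The Key Inclusion Criteria row opens with "Patients who meet all of the following criteria are eligible" and continues into the angiographic list. On this point the list contains:

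- "The lesion(s) must be successfully pre-dilated prior to enrollment";
- a statement that pre-dilatation is mandatory and uses two orthogonal views to confirm the lesion criteria;
- "Successful pre-dilatation of a minimum of 1 Target Lesion", followed by what success means (balloon appearance and balloon sizing);
- "When two target lesions are treated, they must be located in separate major epicardial vessels";
- time windows for intervention in a non-target vessel: at least 30 days before the index procedure or, if planned, at least 6 months after it.

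The Clinical Endpoints row defines TLF as a composite of cardiovascular death, target-vessel MI and clinically indicated target lesion revascularisation. The footnote on target-vessel MI reads "Defined as myocardial infarction not clearly attributed to a non-target vessel". The Statistical Methods row counts TLF once per subject and analyses it by intention to treat.

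**The concern.** For a subject with two target lesions the two lines seem to set different thresholds: one speaks of the lesion or lesions, and the other is satisfied by a single lesion. The sentence in the Study design row uses the singular and does not settle which is meant. On the looser reading, a subject could be randomised after one successful pre-dilatation and the second lesion accepted or dropped as a target afterwards. The trial is described as single-blind without saying who is blinded, so that decision might be taken by someone who knows the arm.

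At stake is which events count. The label decides whether revascularisation of the second lesion, and an MI clearly attributed to its vessel, enter the primary endpoint. Intention to treat fixes which subjects are analysed, not the list of lesions on which their events are counted. If labelling differed by arm, the comparison could be biased in either direction.

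**Working it through.** **Reading the lines together.** Call the line on the lesion or lesions A, and the line asking for at least one B. All criteria must be met.

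| Subject | A met? | B met? | Meets both? |
|---|---|---|---|
| One target lesion, pre-dilated | yes | yes | yes |
| Two target lesions, both pre-dilated | yes | yes | yes |
| Two target lesions, one pre-dilated | no | yes | no |

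A implies B, so B never admits a subject whom A rejects. The count in B still has an ordinary use: subjects may have one or two target lesions, and at least one must qualify for entry. The definition of success attached to B describes a single lesion and suits each target lesion equally.

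The singular in the Study design row adds little to the looser reading. The synopsis also uses the singular for the lesion-length limit and the myocardial-bridge exclusion, which plainly apply to each target lesion. Pre-dilatation is moreover the step used to confirm lesion eligibility, and A places it before enrolment.

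**Could a second lesion be relabelled after allocation?** No supplied text provides for it. The order rule alone would leave a same-session route: a lesion in a separate vessel could be called target or non-target until the first study device is placed. The windows for non-target vessels, if they govern, put any earlier non-target treatment at least 30 days before the index procedure, and so before randomisation. If the Study design row is meant to allow same-session treatment, those two passages need reconciling, which is a separate matter from the pre-dilatation wording.

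**Size if the looser reading were followed anyway.** The inputs from the plan are 444 subjects randomised 1:1 (444/2 = 222 per arm), a one-sided 95% limit by normal approximation, and margin figures of 6 and 8.6%. The synopsis gives no two-lesion share and no expected TLF rate, so the rest is assumed.

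Subjects with a second target lesion, at a 5-15% share: 0.05 × 444 = 22 to 0.15 × 444 = 67. These are exposed, not necessarily affected.

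Shift in the TLF difference = share × fraction labelled differently by arm × 12-month risk of a countable event:

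| Case | Product | Shift (points) | Subjects per 222 |
|---|---|---|---|
| Low | 0.05 × 0.10 × 0.02 = 0.0001 | 0.01 | 0.02 |
| Middle | 0.10 × 0.25 × 0.04 = 0.001 | 0.1 | 0.22 |
| High | 0.15 × 0.50 × 0.08 = 0.006 | 0.6 | 1.33 |

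Against the margins, the high case is 0.6/8.6 = 7% or 0.6/6 = 10%.

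Expected upper limit with equal true rates p in both arms = 100 × 1.645 × √(2p(1 − p)/222):

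| p (assumed) | Upper limit (points) | Plus 0.6 |
|---|---|---|
| 3% | 2.66 | 3.26 |
| 5% | 3.40 | 4.00 |
| 7% | 3.98 | 4.58 |

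All values lie below both margin figures.

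**The case for a change.** The strongest case for acting is that, if A already covers every target lesion, B's count is redundant, and a careful reader may suppose it was written to relax A. Two sites could then act differently in good faith. No supplied line says when the list of target lesions is recorded relative to allocation. The windows for non-target vessels do not dispose of every route either: a second lesion dropped as a target could be deferred to a planned later intervention. If a second lesion were pre-dilated after randomisation, the dissection or calcification exclusions could first arise then. The trial is intended to be pivotal for approval in Japan, and a clarification would be cheap.

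Some of this stands. The wording is untidy, and the synopsis is silent on when the lesion list is recorded. But a redundant line is not a permission, and the post-allocation scenarios require a site to proceed with a subject who fails A. The supplied text is a synopsis that refers to a section 3.4.1 not included here, so details such as the timing of lesion recording may well be set out elsewhere. The bias argument needs three further steps that the text does not supply: a late decision, made with knowledge of the arm, and made differently between arms.

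**Conclusion.** The concern does not call for a change. The two lines are ambiguous for two-lesion subjects but not contradictory. Applied jointly, as the inclusion criteria require, they mean that every designated target lesion is pre-dilated before enrolment. This is a reading of the text, not a view on which procedural rule is clinically preferable.

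If some sites did follow the looser reading, the assumed ranges give a shift of 0.01 to 0.6 points. The top of that range combines three unfavourable assumptions and makes no deduction for the features that dilute it: cardiovascular death counts whatever the label, an MI not clearly attributed to a non-target vessel still counts, and a subject contributes at most one TLF. With equal true rates of 3-7%, the non-inferiority conclusion would be expected to stand against either margin figure. What remains is a missing detail that investigators and analysts can fill sensibly by fixing the target lesions at enrolment and counting TLF on that list. No gain from amending the plan has been shown.
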